Abbreviated Title: Phase 1 IFN + monocytes

Version Date: 12/04/2025

Abbreviated Title: Phase 1 IFN + monocytes

NIH Protocol #: 17-C-0011

Version Date: 12/04/2025

NCT Number: NCT02948426

Title: Phase 1 Study of Intraperitoneal Infusion of Autologous Monocytes with SYLATRON® (Peginterferon alfa-2b) and ACTIMMUNE® (Interferon gamma-1b) in Women with Recurrent or Refractory Ovarian Cancer, Fallopian Tube Cancer or Primary Peritoneal Cancer

NCI Principal Investigator:

[name]., Ph.D.
Women's Malignancies Branch (WMB)
Center for Cancer Research (CCR)
National Cancer Institute (NCI)
National Institutes of Health (NIH)
[name]
[name]
[name]
[contact]
E-mail: [contact]

Drug Name:	Sylatron® (Peginterferon alfa-2b)	Actimmune® (Interferon gamma-1b)	Autologous monocytes
BB-IND Number:	17040	17040	17040
Sponsor:	Center for Cancer Research, NCI	Center for Cancer Research, NCI	Center for Cancer Research, NCI
Manufacturer:	Merck	Horizon Pharma, Inc.	Department of Transfusion Medicine (DTM)

Commercial Agents: None

PRÉCIS

Background:

- Monocytes can differentiate into classic M1 macrophages inhibiting tumor proliferation and promoting natural killer (NK) cell differentiation.
- Human alpha interferons (interferon alfa, IFN α), interferon gamma (IFN γ) and monocytes have strong anti-neoplastic response in vitro and in vivo
- IFN α and IFN γ have been shown in early phase clinical trials to be safely administered intraperitoneally.
- Intraperitoneal monocytes alone or activated with IFN γ are safe and feasible as demonstrated in phase I clinical studies.
- We have shown that the combination of human monocytes, IFN- α 2a and IFN- γ 1b, or pegylated IFN- α , act synergistically against tumor cells in vitro and in mouse models.

Objectives:

- To identify a maximum tolerated dose of intraperitoneal autologous monocytes and Sylatron® (Peginterferon alfa-2b) and Actimmune® (Interferon gamma-1b).

[figure not shown]
Eligibility:

- Advanced metastatic or unresectable epithelial ovarian cancer, primary peritoneal cancer or fallopian tube cancer that is relapsed and resistant or refractory to prior platinum-based standard care systemic regimen.
- Patients must be off prior chemotherapy, radiation therapy, hormonal therapy or biological therapy for at least 4 weeks.
- ECOG performance status 0-1 and adequate organ and marrow function.

Design:

- This is an open label single arm phase I trial to determine the maximum tolerated dose of intraperitoneal monocytes and Sylatron® (Peginterferon alfa-2b) and Actimmune® (Interferon gamma-1b).
- Autologous monocytes obtained through apheresis will be mixed with Sylatron® (Peginterferon alfa-2b) and Actimmune® (Interferon gamma-1b) in a 3 + 3 dose escalation and administered intraperitoneally once every 28 days. A new product will be manufactured for each treatment cycle.
- Once the maximum tolerated dose is obtained, an expansion cohort will be enrolled to better quantify response rate and time to disease progression.
- Research samples including peripheral blood and ascites will be obtained prior to the initiation of study therapy and prior to the start of each cycle. Tissue biopsies will be obtained in the dose expansion phase to characterize the immune infiltration.
- Patients will be evaluated every 2 cycles for response using RECIST v1.1 and every cycle for safety using CTCAE v4.0.

Study Schema

Total Volume (250 mL)

Dose Level	Monocytes total number	SYLATRON ® Peginterferon alfa2b, mcg (final concentration)	ACTIMMUNE ® Interferon gamma-1b, mcg (final concentration)
1	0	25 mcg (0.1 µg/mL)	5 mcg (0.02 µg/mL)
2	$75 \times 10^6 \pm 20\%$	25 mcg (0.1 µg/mL)	5 mcg (0.02 µg/mL)
3	$750 \times 10^6 \pm 20\%$	25 mcg (0.1 µg/mL)	5 mcg (0.02 µg/mL)
3b*	0	250 mcg (1 µg/mL)	50 mcg (0.2 µg/mL)
4	$750 \times 10^6 \pm 20\%$	250 mcg (1 µg/mL)	50 mcg (0.2 µg/mL)

*DL3b will enroll if ≥ 2 subjects enrolled on DL3 or DL4 experience DLT

TABLE OF CONTENTS

PRÉCIS.....	2
TABLE OF CONTENTS	4
STATEMENT OF COMPLIANCE	8
1 INTRODUCTION	8
1.1 Study Objectives.....	8
1.1.1 Primary Objective	8
1.1.2 Secondary Objectives	8
1.1.3 Exploratory Objectives	8
1.2 Background and Rationale	8
1.2.1 Ovarian Cancer	8
1.2.2 Intraperitoneal Interferon.....	9
1.2.3 Intraperitoneal Monocytes	11
1.2.4 Preclinical studies of monocytes combined with both Interferons alpha and gamma	11
1.2.5 Monocytes from women with ovarian cancer	14
2 ELIGIBILITY ASSESSMENT AND ENROLLMENT.....	15
2.1 Eligibility Criteria.....	15
2.1.1 Inclusion Criteria	15
2.1.2 Exclusion Criteria	16
2.1.3 Recruitment Strategies.....	18
2.2 Screening Evaluation.....	18
2.2.1 Screening activities performed prior to obtaining informed consent	18
2.2.2 Screening activities performed after a consent for screening has been signed (Registration Part 1).....	18
2.3 Registration Procedures.....	20
2.3.1 Screen Failures.....	20

The protocol, informed consent form(s), recruitment materials, and all participant materials will be submitted to the Institutional Review Board (IRB) for review and approval. Approval of both the protocol and the consent form must be obtained before any participant is enrolled. Any amendment to the protocol will require review and approval by the IRB before the changes are implemented to the study. In addition, all changes to the consent form will be IRB-approved; an IRB determination will be made regarding whether a new consent needs to be obtained from participants who provided consent, using a previously approved consent form.

1 INTRODUCTION

1.1 STUDY OBJECTIVES

1.1.1 Primary Objective

1.1.1.1 To identify a maximum tolerated dose of intraperitoneal autologous monocytes and Sylatron® (Interferon alfa-2b) and Actimmune® (Interferon gamma-1b).

1.1.2 Secondary Objectives

1.1.2.1 To quantify the response rate and time to disease progression

1.1.3 Exploratory Objectives

1.1.3.1 To characterize the immune infiltration into ascites and tumor (expansion cohort)

1.1.3.2 To analyze circulating leukocyte populations

1.2 BACKGROUND AND RATIONALE

1.2.1 Ovarian Cancer

Ovarian cancer is the leading cause of death due to gynecological malignancies, and the fifth leading cause of death due to cancer in women. Patients are diagnosed late in the course of disease (Stage 3 or 4) due to lack of early symptoms and reliable non-invasive testing. Because of the late diagnosis and aggressiveness of the disease, ovarian cancer results in approximately 14,000 deaths per year. Standard of care for the treatment of ovarian cancer is tumor cytoreductive surgery followed by administration of platinum and taxane based chemotherapy [1]. The disease course is characterized by a high rate of relapse despite an initial good response to the therapy [2]. Patients are classified as chemotherapy sensitive, resistant or refractory. Sensitive patients – who relapse more than 6 months after initial treatment – are re-treated with platinum-based combinations. Without curative second line treatment for patients with resistant or refractory epithelial ovarian cancer (EOC), median survival is 16 months, with most of the population dying within the first two years [3].

Ovarian cancer is largely retained in the peritoneal cavity, with metastases outside of the peritoneum occurring late in disease if at all. In 2006 there was a major advance in the treatment of a portion of the population of women diagnosed with EOC [4]. Patients with stage III optimally resected cancer were given cisplatin IP and paclitaxel IV and IP, compared to standard IV administration of both drugs. There was a 15-month increase in overall survival. This study showed that IP delivery of agents was a viable therapeutic option, and that IP therapy could increase efficacy of treatment.

Adoptive cell therapy was pioneered and developed in the Intramural Research Program. Autologous adoptive cell therapy of tumor infiltrating lymphocytes (TILs) is under development for the treatment of melanoma [5]. TIL therapy is based upon the observations that lymphocytes recognize and kill cancer cells. Based on these observations it was posed that the anti-inflammatory environment of the tumor inhibited a *de novo* immune response. Clinical trials have tested numerous strategies for re-activating lymphocytes, and other leukocyte subsets.

The generation of pharmaceutical grade IFNs in the 1980s generated a large number of human trials aimed at using the anti-viral and anti-neoplastic properties of IFNs [6]. The FDA licensed IFN α -2a and IFN α -2b for treatment of melanoma, hairy cell leukemia, follicular lymphoma, chronic myelogenous leukemia and AIDS related Kaposi's sarcoma. The trials did show greater efficacy than standard of care, and are used as second and third line treatments. Furthermore, it has been shown that activated monocytes are capable of killing malignant cells [7]. While different combinations of IFNs and monocytes were tested in human clinical trials for their tumoricidal properties, the three have never been combined (**Table 1**).

Experimental agents	References
IFN α -2a,2b	[8, 9][10-12]
IFN γ	[13-16]
Monocytes	[17, 18]
IFN γ + monocytes	[19]

Table 1. Clinical development of interferons and monocytes as anti-cancer therapy

1.2.2 Intraperitoneal Interferon

During the late 1980s and 1990s phase one trials were completed testing IP infusion of immune modifying agents, including, but not limited to IFN α or IFN γ for treatment of cancers involving organs in the peritoneal cavity. The large-scale production of cytokines and the production of therapeutic grade lymphocytes through counter-elutriation paved the way for infusion of the cytokines, lymphocytes, and cytokine stimulated lymphocytes for the treatment of malignancies of the peritoneal cavity. Studies focused on, but were not limited to, the treatment of ovarian cancer.

1.2.2.1 Phase I clinical studies

Intraperitoneal (IP) IFN α was used in the first intraperitoneal immunotherapy studies conducted in patients with ovarian cancer. The promising results of these studies, however, were eclipsed by the emergence of taxane based therapies at the time, and have not been taken further than early phase clinical trials. The first Phase 1 study of IP immunotherapy for ovarian cancer evaluated infusion of high dose IFN α -2a as salvage therapy for patients with high grade epithelial ovarian cancer. Of 14 patients receiving IFN α -2a over sixteen weeks, 6 patients (36%) had complete response, one patient (1%) had partial response, and 6 patients (55%) had disease progression [8, 9]. There was found to be an increase in NK cell activity and antibody dependent cell cytotoxic activity in response to IFN α -2a in 11 of the patients that were treated [11]. That trial was followed by a study of 20 patients treated for 8 weeks. Eleven patients (55%) responded, and five of those patients (25%) had complete response. The median duration of complete response was 11 months. The most common adverse effects not requiring dose reduction were fever (80%), abdominal pain (32%), and leukopenia (52%) [12]. In a study with 39 patients with ovarian cancer given intraperitoneal IFN α -2b in combination with chemotherapy, 14/35 patients achieved a pathological CR with only one patient discontinuing treatment due to severe fatigue [10]. In a pharmacokinetics study, IP and blood levels of IFN α -2b were measured after administration. All patients had metastatic disease within the peritoneal cavity and were given a range of IFN α -2b from 5×10^6 units to 15×10^6 units. The bioavailability of IP IFN α -2b was found to be 30 fold higher intraperitoneally compared to in the peripheral blood, with a slower elimination half-life (10-32hr IP compared to 5-13 hours in the peripheral blood) [20].

The first study of high dose IP IFN γ for the treatment of ovarian cancer enrolled 27 patients with relapsed, chemo-resistant disease. Unfortunately, none of the patients on this small trial showed objective response, with 14 patients having progressive disease during the protocol [15]. A follow up of the first IP IFN γ study was published in 1996. A total of 109 patients enrolled. All patients had stage three or greater epithelial ovarian cancer and were given IFN γ either by subcutaneous injection or IP injection through an implanted catheter. Twenty-three patients (23.5%) had a complete response, while 8 (8%) patients had a partial response [16]. In a study with 7 patients treated with IP IFN γ , there was an increase in NK cell activity and tumor-associated lymphocytes and macrophages but no objective responses [14]. A similar study with 8 patients treated with IP IFN γ found similar rises in tumor associated lymphocytes and macrophages: 1 patient with a complete response, 2 with partial responses and 2 with stable disease [13]. Pharmacokinetic studies showed that IFN γ was retained within the peritoneum for longer than 24 hours with up to a 150-200 fold increase in peak levels above that in plasma. All patients who received IP IFN γ $4-8 \times 10^6$ IU/m 2 developed transient fever $\geq 38^{\circ}\text{F}$. Release into the blood was found only in the higher doses ($>2 \times 10^6$ IU/m 2), with a peak level reached in the serum at 6 hours. The peak levels in the peritoneal cavity increased as IFN γ dose increased, with 30.7 IU/mL with 0.05×10^6 IU/m 2 up to 1,720 IU/mL with 8×10^6 IU/m 2) and levels persisted in both the blood and peritoneum for up to 24hr [15]. One of the most important observations from the studies was the tolerable side effect profile, and prolonged intraperitoneal concentrations of IFNs. No published studies report the co-administration of IFNs IP. Together these studies show that IP administration of IFN α or IFN γ is a potentially testable therapeutic treatment.

1.2.3 Intraperitoneal Monocytes

The anti-tumor effect of activated monocytes is well characterized. Monocytes are precursors of resident tissue macrophages, and their functions in normal homeostasis include antigen presentation, phagocytosis of apoptotic cells, and tissue development. [21] Monocytes adapt to their microenvironment and differentiate based on cytokine, chemokine and metabolite expression [22]. In the presence of a tumor, monocytes differentiate into classical M1 macrophages that inhibit tumor proliferation and secrete proinflammatory cytokines and chemokines. They are also able to promote natural killer (NK) cell differentiation, providing a rapid cytotoxic response to tumor cells [18, 23, 24]. This response is further potentiated by the release of IFNs by NK cells, promoting the tumoricidal effects of these cells [25]. Macrophages differentiated towards an M1 phenotype can potentially be exploited in the clinic to selectively target tumor cells without damaging normal tissue [26]. Monocytes can also differentiate into M2 (alternative macrophages) that promote tumor proliferation [27-29] and are associated with a poor prognosis in advanced epithelial ovarian cancer [30]. Therefore, the success of monocytes as an anti-tumor treatment approach may depend on the ability to maintain the M1 phenotype and avoid M2 differentiation in the tumor microenvironment.

Several studies have shown that monocytes can be isolated from the peripheral blood in large numbers (1 billion) and at relatively high purity (80-95%) [31, 32]. Two phase 1 safety trials studied intraperitoneal infusion of autologous monocytes activated with IFN γ or muramyl tripeptide phosphatidylethanolamine (MTP-PE) [19][17]. These studies showed that IP administration of IFN stimulated monocytes was safe and feasible for the treatment of peritoneal carcinoma of colorectal origin. Indium-111 (^{111}In) labeled monocytes were visualized using whole-body Gamma Camera Imaging, and were found to be confined to the peritoneal cavity and not present in the lungs, heart or liver after up to 5 days of monitoring [19]. A subsequent study assessed autologous transplantation of monocytes stimulated with liposomal-muramyl tripeptide phosphatidyl ethanolamine (L-MTP-PE), a potent adjuvant, for the treatment of carcinomas of the peritoneum. Patients' abdomens were imaged at 30 minutes and 7 days post-infusion. Once again, the ^{111}In was confined to the peritoneal cavity with no measurable activity in liver or lungs. Patients experienced low grade toxicities of fevers, chills and abdominal pain. [31]. Response rates were not reported.

1.2.4 Preclinical studies of monocytes combined with both Interferons alpha and gamma

Given the recent successes of immunotherapy in other malignancies, intraperitoneal immunotherapy is a promising area for exploration in cancers predominantly confined to the peritoneal cavity, such as ovarian cancer. Our experimental approach is based on previous observations that IFNs themselves are potent anti-neoplastic proteins [6]. We have shown *in vitro* and in animal models that monocyte stimulation with IFN- α and IFN- γ achieves M1 differentiation, important for anti-tumor activity. These human monocytes, in combination with human alpha interferons (IFN α -2a or pegylated IFN α -2b) and interferon gamma (IFN γ -1b) are potent killers of cancer cell lines *in vitro* [33, 34]. Our studies included 6 ovarian cancer cell lines, and demonstrated that the presence of monocytes additionally decreased viability of some cell lines at low doses of interferons (**Figure 1**) [35]. Our most recent, unpublished work suggests that the mechanism of killing is partially mediated by surface TNF-related apoptosis-inducing ligand (TRAIL) on monocytes that induces cell death via extrinsic apoptosis.

[figure not shown]

Figure 1. IFN activated monocytes are potent killers of ovarian cancer cell lines. Ovarian cancer cells were treated with IFN α -2a and/or IFN γ with or without monocytes. Cell line CaOV3 showed the greatest effect of monocyte addition with either IFN. OVCAR-3 was the most sensitive to the combination of IFNs without monocytes. OVCAR-5 killing was most dependent on the presence of both IFNs and monocytes. Other cell lines showed variable response to the tested combinations. * p<0.05, **p<0.01, ***p<0.001, ****p<0.0001

We expanded this observation to demonstrate that intra-tumoral injection of monocytes with IFNs decreased human ovarian cancer xenograft size (Figure 2) [36]. Importantly, the monocytes introduced into the tumor differentiated into inflammatory M1 macrophages when in the presence of both IFNs (Figure 3).

[figure not shown]

Figure 2 Intratumoral administration of IFNs activated Monocytes inhibited tumor growth and prolonged survival (A) Mice were injected SC with 10×10^6 OVCAR-3 cells and treated with monocytes (3×10^7) or IFN- α 2a and IFN- γ (20 ng each), or combination by i.t. injection on day 0, 15 or 30 post-tumor implantation. Mice receiving combination therapy showed significant inhibition of tumor growth compared to IFNs alone, monocytes alone and PBS. (B) Kaplan-Meier survival curves of mice with OVCAR-3 tumors are shown (n=5 per group). CR, complete regression. Tumor volumes measured by Vernier caliper; survival calculated based on sacrifice

when tumors size reached > 2 cm in diameter. Experiments were repeated twice; bars, SD.

[figure not shown]

Figure 3. IFNs activate differentiation of monocytes to classical (M1) macrophages in OVCAR-3 tumors The tumor samples were collected on day 17 (2 days after 15 day post inoculation treatment, respectively) from the mice in Fig. 1A and the immunofluorescence microscopy were done using antibodies specific for IL-12, CXCL10, NOS2, IL-10, and Arginase-1. Bars, 50 μ m, Magnification X400.

We have shown *in vitro* and in the nude mouse that while IFN α -2a or IFN γ -1b work with monocytes to kill tumor cells, and the combination of all three can achieve the greatest amount of tumoricidal activity. Intratumoral injection of these cells in mice resulted in a reduction in tumor burden and increased overall survival [36]. Additional unpublished data show that IP administration of human monocytes primed with alpha and gamma interferons reduces both tumor burden and ascites volume in a xenograft model of human ovarian cancer (OVCAR3). Furthermore, we demonstrated that monocytes and IFNs improve tumor shrinkage with carboplatin and paclitaxel and significantly increase tumor cell death [35]. Both unpublished and published data strongly suggest that the monocytes must be in contact with the tumor cells for killing. Thus, the rationale for IP immunotherapy is not only to deliver higher concentrations of the drug directly to the tumor, but also to skew monocytes to the M1 phenotype and to activate NK cells in the tumor microenvironment, potentiating tumor cell death.

1.2.5 Monocytes from women with ovarian cancer

We have shown that monocytes isolated through elutriation at the NIH blood bank and monocytes isolated from anti-coagulated peripheral blood from healthy women from the NIH blood bank are capable of killing tumor cells (Figure 4). We have also shown that patients with epithelial ovarian cancer have normal populations of monocytes compared to age matched controls, and the patient monocytes are as effective as healthy age matched control monocytes in killing ovarian cancer cell lines.

[figure not shown]

Figure 4. Monocytes from women with ovarian cancer are equally effective as healthy donors.

Monocytes were isolated from women with ovarian cancer (n=42) or healthy donors (n=23). Viability of ovarian cancer cell line CaOV3 was assessed in the presence of interferons alone or in combination with monocytes from individual sources. *p<0.05, **p<0.01, ****p<0.0001.

Based upon the observations that: (1) the immune system can mount a long and durable response to tumors, (2) human IFN α -2 and IFN γ -1b and monocytes have strong anti-neoplastic response in vitro and in vivo, (3) the IP route of administration is safe, and (4) ovarian cancer is largely confined to the peritoneal cavity, it is likely that the administration of IFNs and monocytes IP will create a strong anti-tumor environment and can overcome the immunosuppressive environment of epithelial ovarian cancer. We hypothesize that the monocyte and interferon administration will be tolerable to women with relapsed ovarian cancer. If successful, this regimen can create a backbone on which to add novel agents such as TRAIL agonists or PD-L1 blockade, in order to increase immune-mediated killing of ovarian cancer.

2 ELIGIBILITY ASSESSMENT AND ENROLLMENT

2.1 ELIGIBILITY CRITERIA

2.1.1 Inclusion Criteria

2.1.1.1 Patients must have histologically or cytologically confirmed advanced metastatic or unresectable epithelial ovarian cancer, primary peritoneal cancer or fallopian tube cancer that is relapsed and resistant (recurred less than 6 months after chemotherapy) or refractory (progressed on chemotherapy) to prior platinum- and taxane-based standard care systemic regimen. Or patients who are not eligible for additional platinum therapy. Histopathologic diagnosis must be confirmed in the Laboratory of Pathology (LP), NCI.

2.1.1.2 Patients must have measurable or evaluable disease. Measurable disease is defined as at least one lesion that can be accurately measured in at least one dimension (longest diameter to be recorded for non-nodal lesions and short axis for nodal lesions) as ≥ 20 mm with conventional techniques or as ≥ 10 mm with spiral CT scan. See Section 6.3 for the evaluation of measurable disease. Evaluable disease includes CA125, ascites, peritoneal carcinomatosis, as defined in Section 6.3.1.

- 2.1.1.3 Patients must be at least 4 weeks from previous therapy (chemotherapy, hormonal therapy, and radiation therapy, immunotherapy and monoclonal antibodies, alternative therapy or investigational therapeutic agents). There is no limitation on the amount of prior therapies allowed. Patients with ovarian cancer 4 weeks from previous therapy have been found to have normal monocyte function (unpublished).
- 2.1.1.4 Patients who have had cranial radiation therapy need to have completed it \geq 8 weeks prior to enrollment.
- 2.1.1.5 Patients are permitted to receive investigational imaging agents while on study.
- 2.1.1.6 Patients who have had major surgery must be fully recovered and require a recovery period of \geq 4 weeks prior to enrolling on study.
- 2.1.1.7 Age \geq 18 years. Because no dosing or adverse event data are currently available on the use of intraperitoneal monocytes, IFN α 2 or IFN γ in patients $<$ 18 years of age, children are excluded from this study, but will be eligible for future pediatric trials.
- 2.1.1.8 ECOG performance status \leq 1 (Karnofsky \geq 70%, see [Appendix A](#)).
- 2.1.1.9 Adequate renal function, defined as serum creatinine \leq 1.5 X upper limit of normal (ULN), or measured creatinine clearance \geq 60 mL/min/1.73m 2 .
- 2.1.1.10 Adequate hepatic function, defined as AST and ALT levels \leq 3 X ULN and total bilirubin $<$ 1.5 X ULN, unless known diagnosis of Gilbert's syndrome, where bilirubin \leq 5 mg/dl will be permitted. Gilbert's syndrome will be defined as elevated unconjugated bilirubin, with conjugated (direct) bilirubin within the normal range and less than 20% of the total. Total bilirubin will be permitted up to 5 mg/dl, if patients have historical readings consistent with the definition of Gilbert's syndrome prior to entering study.
- 2.1.1.11 Adequate bone marrow function, defined as absolute neutrophil (ANC) \geq 1,500/mm 3 (\geq 1.5 X10 6 /L), platelet count \geq 75,000/mm 3 (\geq 75 X10 6 /L), and hemoglobin \geq 8 g/dL (transfusion to obtain hemoglobin \geq 8 g/dL is allowed).
- 2.1.1.12 The effects of intraperitoneal monocytes, IFN α 2, and IFN γ on the developing human fetus are unknown. For this reason and because interferons based on animal data may cause fetal harm, women of child-bearing potential (excludes women with recurrent ovarian cancer) and men must agree to use adequate contraception (hormonal or barrier method of birth control; abstinence) prior to study entry and for the duration of study participation. Should a woman become pregnant or suspect she is pregnant while she is participating in this study, she should inform her treating physician immediately.
- 2.1.1.13 Ability of subject to understand and the willingness to sign a written informed consent document.

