2.1.2 Exclusion Criteria

- 2.1.2.1 Patients who are receiving any other investigational agents (with exception of imaging agents as indicated above in section [2.1.1.5](#)).
- 2.1.2.2 Patients cannot have previously been treated with interferons (e.g., for chronic active hepatitis).
- 2.1.2.3 Lack of recovery of prior adverse events to Grade \leq 1 severity (National Cancer Institute Common Terminology Criteria for Adverse Events [NCI CTCAE] v 4.03) (except alopecia) due to therapy administered prior to the initiation of study drug dosing. Stable

persistent grade 2 peripheral neuropathy may be allowed as determined on a case-by-case basis at the discretion of the Investigator as interferon has not been shown to cause or exacerbate peripheral neuropathy.

- 2.1.2.4 Patients with active infection will not be eligible, but may become eligible once infection has resolved and at least 7 days have elapsed after antibiotics use was completed.
- 2.1.2.5 Concomitant chronic (daily or almost daily for ≥ 1 month prior) use of steroids or non-steroidal anti-inflammatory drugs (NSAIDS).
- 2.1.2.6 Patients with a recent history (within last 5 years) of autoimmune disease or inflammatory diseases will be excluded, because interferons may worsen these conditions. Exceptions will be allowed for vitiligo and hypothyroidism that has been stable on thyroid replacement medications for >6 weeks.
- 2.1.2.7 Impaired cardiac function or clinically significant cardiac disease including the following:
 - New York Heart Association class III or IV congestive heart failure
 - Myocardial infarction within the last 12 months
 - Subjects known to have impaired LVEF according to institutional standards
- 2.1.2.8 History of allergic reactions attributed to compounds of chemical or biologic composition similar to interferons or other agents used in the study.
- 2.1.2.9 Uncontrolled intercurrent illness including, but not limited to, ongoing or active infection, symptomatic congestive heart failure, unstable angina pectoris, cardiac arrhythmia, or psychiatric illness/social situations within the last 12 months that would limit compliance with study requirements. Patients with history of neuropsychiatric disorders or Major Depressive Disorder (DSM 5 definition:

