Assessment of disease by imaging (may include CT chest, abdomen and pelvis)	Within 28 days prior to treatment
Ophthalmic evaluation including visual acuity and funduscopic examination performed by an ophthalmologist	Within 180 days (-14 days) prior to treatment
Assessment of venous access in Department of Transfusion Medicine	Anytime prior to apheresis
Intraperitoneal catheter placement in Interventional Radiology, if not already placed OR surgical implantation of intraperitoneal port by Gynecologic Oncology if not already placed OR verification by clinicians of functional IP catheter or IP port (if pre-existing)	X
CBC with differential and platelet count	X
Metabolic panel (magnesium, calcium, albumin, phosphorus)	X
Acute care panel (electrolytes, glucose, BUN, creatinine)	X

Assessment	Timeframe (calendar days)
	Within 7 days prior to treatment (unless otherwise noted)
Hepatic function tests (AST/ALT/total bilirubin)	X
CA125	X
β-HCG in women of childbearing potential	X

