14 PHARMACEUTICAL INFORMATION

14.1 PEGINTERFERON ALFA-2B (SYLATRON)

Merck Sharp & Dohme Corp., a subsidiary of Merck & Co., Inc., Whitehouse Station, NJ

Source: The agent will be obtained from Merck through Clinical Trials Agreement (CTA) #01047.

For the commercial product given subcutaneously, product labeling is prefaced by a boxed warning that identifies adverse reactions, including: depression and other neuropsychiatric disorders. The most common adverse reactions described in product labeling (>60%) include: fatigue, increased AST, increased ALT, pyrexia, anorexia, myalgia, nausea, chills and injection site reactions.

Contraindications include known hypersensitivity reactions to peginterferon alfa-2b or interferon alfa-2b, autoimmune hepatitis, and hepatic decompensation with Child-Pugh scores >6 (classes B and C).

Drug interactions: Drug metabolized by cytochrome P-450 (CYP) enzymes: Monitor closely when used in combination with drugs metabolized by CYP1A2 and/or CYP2D6.

Formulation and Preparation: commercially marketed SYLATRON™ vials nominally labeled to contain 200-mcg and 300-mcg vials are overfilled to contain 296 mcg and 444 mcg lyophilized peginterferon alfa-2b, respectively. When each vial is reconstituted with 1 mL Sterile Water for Injection, USP, the resulting concentrations are approximately 296 mcg/mL and 444 mcg/mL, respectively.

Refer to the package insert for additional information.

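### The eligibility criteria do not fully carry over the hepatic contraindications in section 14.1: decompensation is not addressed, and autoimmune hepatitis is covered only within a 5-year window

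*Combined protocol and SAP*

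**What the plan says.** Section 14.1 gives three contraindications to peginterferon alfa-2b. The first is known hypersensitivity. The other two are hepatic: "autoimmune hepatitis, and hepatic decompensation with Child-Pugh scores >6 (classes B and C". Neither hepatic item carries a time limit, and the sentence is not confined to the subcutaneous route.

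The hepatic entry criterion, 2.1.1.10, starts "Adequate hepatic function, defined as AST and ALT levels". It caps both enzymes at 3 times the upper limit of normal and total bilirubin below 1.5 times that limit. It has one exception: "Total bilirubin will be permitted up to 5 mg/dl, if patients have historical readings consistent with the definition of Gilbert's syndrome".

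On autoimmune disease, exclusion 2.1.2.6 reads "Patients with a recent history (within last 5 years) of autoimmune disease or inflammatory diseases will be excluded, because interferons may worsen these conditions". It then adds: "Exceptions will be allowed for vitiligo and hypothyroidism that has been stable on thyroid replacement medications". Autoimmune hepatitis is not among the exceptions.

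The liver line of the Screening Part 2 table in section 2.2.2 is "Hepatic function tests (AST/ALT/total bilirubin", and the baseline table in section 2.5 repeats it. Albumin is drawn in the metabolic panel in both tables, but no criterion uses it. Neither table lists a coagulation test or a liver score.

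**The concern.** The protocol's drug section and its eligibility section do not describe the same excluded population. Read literally, the written criteria do not screen for a condition that the drug section treats as a reason not to give the agent.

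This is more than a missing cross-reference. Section 12.5.1.1 sends the reader to section 14 for the risks of treatment, and section 12.4 counts eligibility screening among the measures that protect against those risks. A contraindication in section 14 with no counterpart in section 2.1 leaves that protection incomplete on paper. The protocol also does not treat the subcutaneous product label as irrelevant to intraperitoneal use, because exclusion 2.1.2.9 bars certain neuropsychiatric histories expressly on the strength of the label's boxed warning. Silence on the hepatic items therefore cannot be taken as a decision that they do not apply.

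What is at stake is patient safety and consistent screening decisions, not the statistical design.

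**Working it through.** No formula applies, since the point depends on no sample size, power or event count. The check sets each contraindication in 14.1 against the inclusion and exclusion criteria (2.1.1, 2.1.2), the screening and baseline tables (2.2.2, 2.5) and the donor-testing text in Appendix B.

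| Contraindication in 14.1 | Matching criterion | Screening or baseline item | What is left open |
|---|---|---|---|
| Hypersensitivity | 2.1.2.8 (allergy to interferon-like or other study agents) | History | Nothing material |
| Autoimmune hepatitis, no time limit | 2.1.2.6, last 5 years only | History; AST and ALT | A history confined to more than 5 years ago |
| Hepatic decompensation with Child-Pugh above 6 | None | AST, ALT and bilirubin with limits; albumin with no limit | The condition is neither named nor assessed |

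1. **Autoimmune hepatitis.** The exclusion covers autoimmune disease generally and makes only two exceptions, so active or recent autoimmune hepatitis is excluded without being named. The only difference from 14.1 is the look-back window.

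2. **Hepatic decompensation.** Criterion 2.1.1.10 limits two enzymes and bilirubin. Section 14.1 frames its contraindication as decompensation with a Child-Pugh score. The documents do not equate the two, and no other criterion mentions decompensation or the score.

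3. **The general exclusion.** Criterion 2.1.2.9 begins "Uncontrolled intercurrent illness including, but not limited to, ongoing or active infection, symptomatic congestive heart failure". Its list is open-ended, so an investigator could use it for liver failure, but none of its examples is a liver disease and it requires no assessment.

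4. **Other partial safeguards.** Appendix B requires negative hepatitis C serology and hepatitis B surface antigen for product handling. Dose Level 4, used in the expansion cohort, contains cells, so this applies there. It addresses viral hepatitis, not decompensation or autoimmune hepatitis. Exclusion 2.1.2.5 removes chronic steroid users. Section 14.1 refers to the package insert for further information.

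The count is one contraindication matched, one matched except for a window, and one not matched.

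**The case against.** The strongest reply is that the gap is mostly theoretical. A woman with decompensated liver disease would have to pass the enzyme and bilirubin limits, a platelet floor of 75,000/mm³, ECOG 0-1, history, physical examination and imaging. The investigator could still invoke 2.1.2.9 or the package insert. Escalation has concluded, and the plan is for ten further patients at Dose Level 4. All of this stands as a reason to rate the point low. It does not remove the mismatch, because none of these provisions names decompensation or requires that it be assessed.

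A reader might also infer three stronger things that the documents do not support:

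- **That autoimmune hepatitis is not screened at all.** This would be true only if 2.1.1.10 were read alone. Exclusion 2.1.2.6 already handles current and recent disease.
- **That a patient with marked ascites and low albumin is therefore contraindicated.** The documents do not give the components or points of the score, so no total can be built from them. Section 14.1 also ties the score to hepatic decompensation. In this population ascites is accepted as evaluable disease (2.1.1.2), and ascites or low albumin may come from the cancer rather than from liver failure.
- **That such enrolments would distort the toxicity estimate at Dose Level 4.** Under 3.1.1, grade 3 or higher transaminitis is dose-limiting only if it lasts more than 7 days. Sections 8.1.5 and 8.2 require relatedness to be recorded, and an alternate etiology where an event is judged unrelated. The documents give no basis for saying how often this would arise.

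**Conclusion.** The point holds in a narrow form. The eligibility criteria do not address hepatic decompensation, which 14.1 lists as a contraindication, and they cover autoimmune hepatitis only where there is a history in the last 5 years. It is a minor safety reconciliation, with no effect on sample size, power or analysis.

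The number of patients affected cannot be derived from the documents. For decompensation it would depend partly on how cancer-related ascites and low albumin are read. The conclusion rests on the protocol text alone and assumes that the contraindications in 14.1 are meant to apply to intraperitoneal use, since nothing in the protocol says otherwise.

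**What to change.** Reconcile section 2.1 with section 14.1 in one of two ways:

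- have the eligibility criteria reflect the hepatic contraindications that the protocol lists, including the look-back window for autoimmune hepatitis; or
- state in the protocol why they do not apply to the intraperitoneal route.

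If a liver score is used at entry, state how ascites and low albumin attributable to the cancer are read. Otherwise the rule could be applied inconsistently in a population where ascites is accepted as evaluable disease. Which clinical limit is right is for the sponsor to decide.

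The cost is one or two eligibility lines. Bilirubin and albumin are already drawn at screening, and some added laboratory work may be needed if a score is adopted. No analysis or sample-size text changes.
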